Esophageal Cancer is one of the few cancers increasing in frequency in the US with 18,170 cases estimated for 2014. Unfortunately, the majority of these patients will ultimately die of their disease as the 5-year survival rate for all stages combined is 17%. The majority of these cancers are now adenocarcinomas of the distal esophagus and GE junction. Fortunately, more of these are being detected at an earlier stage when the chance of cure increases to over 50%. We perform over 50 esophagectomies each year at UVA and the majorities are now performed in a multidisciplinary fashion including treatment with chemotherapy and radiation.

The risk of lung and esophageal cancer recurrence varies widely from 30% to 75% and our group, along with others, has shown that recurrence depends upon a variety of tumor and patient related factors. For those patients whose recurrences are detected early, there is a possibility for long-term survival following redo surgical resection, radiation therapy or chemotherapy. However, the majority of patients with recurrence will not be candidates for curative treatment. Therefore, many patients undergo repeated surveillance testing to identify one patient whose survival can be meaningfully prolonged.

IRB-HSR# 17525 A Study of Patient-reported Outcomes in Patients with Lung or Esophageal Cancer

Therefore, the optimization of post treatment surveillance following lung or esophageal cancer resection is a national priority. The goal is to create a personalized decision support tool for lung and esophageal cancer surveillance that tailors follow-up to an individual patient. The decision tool incorporates risk-stratification for recurrence and survival, patient reported outcomes, and patient preferences to inform lung cancer survivors and their healthcare providers when selecting a surveillance strategy.

This observational study will look to see if the PROMIS score for each patient directly reflects the state of their disease by using these three disease states, no recurrence, asymptomatic with recurrence, symptomatic with recurrence.

Hypothesis to be Tested

Hypothesis: Patient reported outcomes will vary according to the presence of recurrence or metastasis in patients with lung or esophageal cancer.

Study Design: Biomedical

1. Will controls be used?

No

2. What is the study design?

Observational study

3. Does the study involve a placebo?

No

Human Participants

Ages: ≥18

Sex: Male or Female

Race: Any

Subjects- see below

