1. Provide target # of subjects (at all sites) needed to complete protocol.

400

2. Describe expected rate of screen failure/ dropouts/withdrawals from all sites.

Expected rate of screen failures or dropouts is thought to be very low <%1

3. How many subjects will be enrolled at all sites?

400

4. How many subjects will sign a consent form under this UVa protocol?

400

5. Provide an estimated time line for the study.

IRB-HSR# 17525 A Study of Patient-reported Outcomes in Patients with Lung or Esophageal Cancer

50% enrollment in 6 months, 100% enrollment by end of year 1. There will be ongoing analysis of the data during the conduct of this trial.

Inclusion/Exclusion Criteria

1. List the criteria for inclusion

- ≥ 18 years of age
- Suspected or Known diagnosis of lung or esophageal cancer
- Willing and able to complete questionnaires
-

2. List the criteria for exclusion

- Subjects unwilling to provide informed consent
- Subjects unwilling or unable to answer the questionnaires

3. List any restrictions on use of other drugs or treatments.

None

Statistical Considerations

1. Is stratification/randomization involved?

NO

2. What are the statistical considerations for the protocol?

This is an observational pilot study to obtain patient reported outcomes for lung and esophageal cancer.

3. Provide a justification for the sample size used in this protocol.

The thoracic surgery and medical oncology clinics at UVa performed over 1,000 follow-up visits in 2012 for patients following lung and esophageal cancer resection. This pilot study will enroll 200 patients for integration of PCOR (Patient Centered Outcomes Research) score into their electronic medical record. A sample size of 150 patients is enough to detect a difference of 3.2 points on the PROMIS scale between each of the three groups (asymptomatic without recurrence, asymptomatic with recurrence, and symptomatic) with 80% power at the 5% significance level. (i.e.: if asymptomatic without recurrence averages 56.4, asymptomatic with recurrence averages 53.2 and, symptomatic with recurrence averages 50).

4. What is your plan for primary variable analysis?

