This is an observational study to determine PROMIS scores at various time points. We will not be using repeated measures for this primary variable as each patient will only contribute one data point. We will calculate a mean and SD for each of the three disease states, no recurrence, asymptomatic with recurrence, symptomatic with recurrence.

5. What is your plan for secondary variable analysis?

We may do some longitudinal analysis of patient reported outcomes and will then account for repeated measures.

IRB-HSR# 17525 A Study of Patient-reported Outcomes in Patients with Lung or Esophageal Cancer

6. Have you been working with a statistician in designing this protocol?

Yes, [name]

Biomedical Research

1. What will be done in this protocol?

Enrolled subjects will be asked to complete an on-line (web-based) survey using an iPad or computer during a regularly scheduled clinic visit. This survey is estimated to take 10-15 min. Most patients will only be asked to complete this survey once, but some patients will be asked to answer the questions a second or third time during a regularly scheduled clinic visit for follow up of their esophageal or lung cancer.

Patients will provide their age, race, ethnicity and sex at the beginning of the survey. They will be provided a unique study identifier (i.e., 001, 002 etc.) and a password that they can use to complete the survey. Only the patient will have access to the password and no HIPPA identifiers are collected in the PROMIS on-line system. A Private web browser will be used to access the PROMIS website for each patient, so that all web browsing activity is removed after each patient completes the survey. A member of the research team will be responsible for closing the web based session in order to make sure all browsing history is erased properly."

Data will then be collected from the STS Society of Thoracic Surgeons database for subjects who complete the on-line survey. The STS database is a national quality improvement database which the University of Virginia participates in for clinical purposes. Local data from the STS database will be queried for subjects who are enrolled in this study to provide clinical information about the patients clinical condition. The PROMIS reports and the STS data that links clinical information with the PROMIS data will be stored on a HIPPA compliant UVA server (surgery O: drive). This data will be accessible only to members of this research team.

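### The primary summary pools lung and esophageal patients within each disease state, so a difference between the cancers could be mixed with the recurrence effect if the mix varies across states

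*Combined protocol and SAP*

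**What the plan says.** Statistical Considerations, item 4, describes the whole primary analysis: "We will calculate a mean and SD for each of the three disease states, no recurrence, asymptomatic with recurrence, symptomatic with recurrence". Each patient contributes one data point. Item 5 adds only an optional secondary analysis: "We may do some longitudinal analysis of patient reported outcomes and will then account for repeated measures". Neither item, nor the sample-size justification in item 3, mentions cancer type.

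The eligibility criterion covers both cancers: "Suspected or Known diagnosis of lung or esophageal cancer". No quota or expected share of either is given. The hypothesis is also joint: "Patient reported outcomes will vary according to the presence of recurrence or metastasis in patients with lung or esophageal cancer".

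The Background describes the treatment of the two cancers differently. For limited non-small cell lung cancer, surgery is presented as the main route to cure. Of esophagectomies at the site it says that "the majorities are now performed in a multidisciplinary fashion including treatment with chemotherapy and radiation". It also reports for esophageal cancer that "the 5-year survival rate for all stages combined is 17" per cent. Recurrence is given as a single range for both cancers: "The risk of lung and esophageal cancer recurrence varies widely from 30% to 75" per cent, attributed to tumor and patient factors.

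Diagnosis is among the items to be taken from the STS database (Biomedical Research, item 2), but no analysis is said to use it.

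**The concern.** The hypothesis is a comparison between disease states, and item 3 justifies the sample size by gaps of 3.2 points between their means. Disease state is observed, not assigned, so nothing in the design balances cancer type across the three states. If one cancer recurs more often than the other, it takes a larger share of the recurrence states than of the no-recurrence state. If patients with that cancer also score differently for reasons unrelated to recurrence, the pooled contrast picks up part of that difference. Depending on direction, it could look like a recurrence effect or hide one.

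A second issue does not depend on bias. The Background aims at a surveillance tool for both cancers that is tailored to the individual patient. A single pooled mean per state cannot show whether PROMIS tracks disease state in lung cancer, in esophageal cancer, or in both.

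**Working it through.** **Planned gaps (item 3).** The assumed means are 56.4, 53.2 and 50. The gaps are 56.4 − 53.2 = 3.2, 53.2 − 50 = 3.2, and 56.4 − 50 = 6.4 points. Item 3 states no SD or test, so its 150 patients cannot be reproduced from the document alone. With an assumed SD of 10 and three groups of 50, an overall F-test has 81.7% power, which fits the stated 80%. The pooling point does not depend on that figure.

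**Formula.** Let D be the number of points by which esophageal patients score lower than lung patients, taken as equal in every state. Let p be the esophageal share of a state. The pooled gap between no recurrence and recurrence equals the true gap plus

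shift = D × (p with recurrence − p without recurrence).

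The shift is zero if D = 0 or if the shares are equal. Both conditions must fail for bias to arise.

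**Inputs.** From the documents: 400 patients in total (Human Participants), and recurrence between 30% and 75% (Background, not split by cancer). Assumed: 300 lung and 100 esophageal patients; D of 3 to 5 points; the recurrence risks per cancer below; the same esophageal share in both recurrence states; and recurrence risk standing in for the proportion with recurrence at the time of the survey.

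| Recurrence risk, lung / esophageal | Esophageal share with recurrence | Esophageal share without | Difference | Shift, D = 3 | Shift, D = 5 |
|---|---|---|---|---|---|
| Equal | 25% | 25% | 0 | 0 | 0 |
| 40% / 60% | 60/180 = 33.3% | 40/220 = 18.2% | 0.152 | 0.45 | 0.76 |
| 30% / 75% | 75/165 = 45.5% | 25/235 = 10.6% | 0.348 | 1.04 | 1.74 |
| 60% / 40% | 40/220 = 18.2% | 60/180 = 33.3% | −0.152 | −0.45 | −0.76 |
| 75% / 30% | 30/255 = 11.8% | 70/145 = 48.3% | −0.365 | −1.10 | −1.83 |

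A positive shift widens the pooled gap and can pass for a recurrence effect. A negative shift narrows it and can hide one.

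**Against the planned gaps, at the 30% / 75% extreme.**
- No recurrence versus asymptomatic recurrence: 1.04/3.2 = 33% to 1.74/3.2 = 54%.
- No recurrence versus symptomatic recurrence: 1.04/6.4 = 16% to 1.74/6.4 = 27%.
- Asymptomatic versus symptomatic recurrence: zero, because the share is assumed equal in both.

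At 40% / 60% the first of these falls to 0.45/3.2 = 14% and 0.76/3.2 = 24%.

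**Sensitivity to the mix.** At 30% / 75% and D = 5, the shift is 0.90, 1.51, 1.92 and 2.26 points for overall esophageal shares of 10%, 20%, 30% and 50%. For the shift to reach 3.2 points at the assumed 25% share, D would have to be 3.2/0.348 = 9.2 points.

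**Effect on a test, if one were used.** Assume SD 10, 50 per group, and a two-sided pairwise comparison at 5%. With no true difference, a shift of 0.5, 1.0 or 1.6 points raises the rejection rate to 5.7%, 7.9% or 12.6%. A 1.6-point shift in the opposite direction lowers power for a true 3.2-point gap from 36% to 12%.

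**The case against.** The strongest objection is that the documents establish neither condition for bias. They give one recurrence range for both cancers and never say which recurs more often. They give no PROMIS level for either cancer. A reader might infer from the Background that esophageal cancer recurs more often and scores worse, and that the primary comparison is therefore biased by a third to a half of the target difference. The documents do not support this. The 17% survival figure covers all stages, is followed by a chance of cure above 50% for disease found earlier, and has no lung figure beside it. The 33% to 54% result needs the widest split the range allows and applies to one of the three contrasts. Eligibility also admits suspected cases, and risk over follow-up is not the proportion with recurrence at one visit. All of this stands, and it limits the point to a conditional one.

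Two further objections stand in part. First, this is a pilot with a descriptive primary output, and no test or model is named, so there is no specified model to adjust. That lowers the severity. But the hypothesis and the 3.2-point justification are both comparisons between states, and summaries by cancer need no model. Second, stage and comorbidities are collected and equally unused, and the documents do not show that cancer type matters more. That is true, but the two cancers are named in the hypothesis and in the aim of the surveillance tool, which gives cancer type a claim of its own.

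The question "Is stratification/randomization involved" is answered no. This reads as a statement about design, and it does not show that analysis by cancer was ruled out.

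**Conclusion.** The point holds as a conditional one. The plan pools the two cancers within each disease state, and nothing in the design or analysis keeps a cancer-type difference out of the disease-state contrast. Bias follows only if the mix differs across states and scores differ between the cancers within a state. Its size and direction cannot be fixed from the documents. Under the assumed 300/100 split and a 3 to 5 point cancer difference, its size runs from nothing to between 1 and 2 points in either direction in the no-recurrence versus recurrence contrast, against planned gaps of 3.2 and 6.4 points.

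The loss of information does not rest on those assumptions: pooled means cannot show whether the relation holds in each cancer. The pilot status and the missing inputs make this an improvement worth making, not a flaw that invalidates the study.

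**What to change.** In Statistical Considerations, item 4:

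1. Keep the pooled mean and SD per disease state.
2. Add mean, SD and number of patients by disease state within each cancer, using the STS diagnosis field.
3. State that any overall disease-state comparison will come from an analysis with a cancer-type term.

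If the difference between the cancers is the same in every state, the cancer-type term removes the shift. If it is not, the within-cancer summaries will help to show that. The wording should be settled in advance, because the timeline (Human Participants, item 5) foresees analysis while the study runs.

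The cost is text only: no new data, visits or patients. The downside is precision within each cancer, especially esophageal. For example, with an assumed SD of 10, a mean from 25 esophageal patients without recurrence (the 30% / 75% case) has a 95% interval of about ±1.96 × 10/√25 = ±3.9 points. The pooled 235 give ±1.96 × 10/√235 = ±1.3 points. The within-cancer results should therefore be presented as descriptive.

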1.1 How will you define adverse events (AE)?

Do not change this answer

An adverse event will be considered any undesirable sign, symptom or medical condition considered **related to the intervention**. Medical condition/diseases present before starting the intervention will be considered adverse events only if

IRB-HSR# 17525 A Study of Patient-reported Outcomes in Patients with Lung or Esophageal Cancer

they worsen after starting the study and that worsening is considered to be related to the study intervention. An adverse event is also any undesirable and unintended effect of research occurring in human subjects as a result of the collection of identifiable private information under the research.

1.2 How will you define an unanticipated problem?

Do not change this answer

An unanticipated problem is any issue that involves increased risk(s) to participants or others. This means issues or problems that cause the subject or others to be placed at greater risk than previously identified, even if the subject or others do not incur actual harm. For example if a subject's confidentiality is compromised resulting in serious negative social, legal or economic ramifications, an unanticipated problem would need to be reported. (e.g. serious loss of social status, loss of job, interpersonal conflict.)

1.3 What is the definition of a protocol violation?

Do not change this answer

A protocol violation is defined as any change, deviation, or departure from the study design or procedures of a research project that is NOT approved by the IRB-HSR prior to its initiation or implementation, OR deviation from standard operating procedures, Good Clinical Practices (GCPs), federal, state or local regulations. Protocol violations may or may not be under the control of the study team or UVa staff. These protocol violations may be major or minor violations.

Additional Information: see the IRB-HSR website at

http://www.virginia.edu/vpr/irb/HSR_docs/Forms/Protocol_Violations_%20Enrollment_Exceptions_Instructions.doc

1.4 What is the definition of a data breach?

Do not change this answer

A data breach is defined in the HITECH Act (43 USC 17932) as an unauthorized acquisition, access, or use of protected health information (PHI) that compromises the security or privacy of such information.

Additional Information may be found on the IRB-HSR Website: [Data Breach](#)

2. What risks are expected due to the intervention in this protocol?

Expected Risks related to study participation	Pick One
There is a small risk that breaches of privacy and/or confidentiality might occur. The risk of violation of subject privacy and	Occurs rarely

IRB-HSR# 17525 A Study of Patient-reported Outcomes in Patients with Lung or Esophageal Cancer

confidentiality is minimal due to the requirements of the privacy plan in this protocol.	
--	--

3. When will recording and reporting of unanticipated problems/adverse events begin?

After subject signs consent

4. When will the recording/reporting of unanticipated problems/adverse events end?

Subject completes participation in the protocol

5. What is your plan for safety monitoring?

Do not change this answer

Safety monitoring and aggregate review of adverse events, unanticipated problems, protocol violations and any data breach will be performed by the PI and IRB-HSR through continuation review at least annually.

6. What is your plan for reporting a Unanticipated Problem, Protocol Violation or Data Breach?

Do not change this answer

Type of Event	To whom will it be reported:	Time Frame for Reporting	How reported?
Unanticipated Problems that are not adverse events or protocol violations This would include a Data Breach.	IRB-HSR	Within 7 calendar days from the time the study team received knowledge of the event.	Unanticipated Problem report form. http://www.virginia.edu/vprgs/irb/HSR_docs/Forms/Reporting_Requirements-Unanticipated_Problems.doc
Protocol Violations (The IRB-HSR only requires that MAJOR violation be reported, unless otherwise required by your sponsor, if applicable.) OR Enrollment Exceptions	IRB-HSR	Within 7 calendar days from the time the study team received knowledge of the event.	Protocol Violation and Enrollment Exception Reporting Form http://www.virginia.edu/vprgs/irb/hsr_forms.html Go to 3rd bullet from the bottom.

IRB-HSR# 17525 A Study of Patient-reported Outcomes in Patients with Lung or Esophageal Cancer

Data Breach of Protected Health Information	The UVa Corporate Compliance and Privacy Office ITC: if breach involves electronic data UVa Police if breach includes items that are stolen	As soon as possible and no later than 24 hours from the time the incident is identified. As soon as possible and no later than 24 hours from the time the incident is identified. IMMEDIATELY.	UVa Corporate Compliance and Privacy Office- [contact] ITC: Information Security Incident Reporting procedure, http://www.itc.virginia.edu/security/reporting.html Police: phone- [contact]
--	---	--	--

Risk/ Benefit Analysis

1. What are the potential benefits for the participant as well as benefits which may accrue to society in general, as a result of this study?

There are no expected direct benefits for individual participants in this study. However, future patients with lung or esophageal cancer may benefit as a result of information learned in this research. The risks in this study are considered minimal and related to risk to privacy and confidentiality. The risks are minimized by the privacy plan outlined in this study. The risks are outweighed by the potential benefits this could bring. We believe if this study shows a correlation between patient reported outcomes and their clinical presentation, this could potentially play a role in the development of patient specific cancer surveillance tools.

2. Do the anticipated benefits justify asking subjects to undertake the risks?

The potential benefits to cancer surveillance do justify the minimal risk this study poses.

Bibliography

2. Cancer Facts & Figures. 2013. (Accessed July 26, 2013, at <http://www.cancer.org/research/cancerfactsstatistics/index.>)
4. Darling GE, Allen MS, Decker PA, Ballman K, Malthaner RA, Ingle J, Jones DR, McKenna RJ, Landreneau RJ, Rusch VW, Putnam JB. Randomized trial of mediastinal lymph node sampling versus complete lymphadenectomy during pulmonary resection in the patient with N0 or N1 (less than hilar) non-small cell

APPENDIX: Legal/Regulatory

Recruitment

The following procedures will be followed:

- Finders fees will not be paid to an individual as they are not allowed by UVa Policy.
- All recruitment materials will be approved by the IRB-HSR prior to use. They will be submitted to the IRB after the IRB-HSR has assigned an IRB-HSR # to the protocol.
- Only those individuals listed as personnel on this protocol will recruit and or conduct the consenting process with potential subjects.

Retention Incentives

Any item used by the sponsor/ study team to provide incentive to a subject to remain in the study, other than compensation identified in the Payment section, will be submitted to the IRB for review prior to use. The IRB-HSR will provide the study team with a Receipt Acknowledgement for their records. Retention incentive items are such things as water bottles, small tote bags, birthday cards etc. Cash and gift cards are not allowed as retention incentives.

Clinical Privileges

The following procedures will be followed:

- Investigators who are members of the clinical staff at the University of Virginia Medical Center must have the appropriate credentials and been granted clinical privileges to perform specific clinical procedures whether those procedures are experimental or standard.
- The IRB cannot grant clinical privileges.
- Performing procedures which are outside the scope of the clinical privileges that have been granted may result in denial of insurance coverage should claims of negligence or malpractice arise.

IRB-HSR# 17525 A Study of Patient-reported Outcomes in Patients with Lung or Esophageal Cancer

- Personnel on this protocol will have the appropriate credentials and clinical privileges in place before performing any procedures required by this protocol.
- Contact the Clinical Staff Office- [name] or [name] for further information.

Sharing of Data/Specimens

Data and specimens collected under an IRB approved protocol are the property of the University of Virginia. You must have “permission” to share data/ specimens outside of UVa other than for a grant application and or publication. This “permission” may come in the form of a contract with the sponsor or a material transfer agreement (MTA) with others. A contract/ MTA is needed to share the data outside of UVa even if the data includes no HIPAA identifiers and no code that could link the data back to a HIPAA identifier.

- No data will be shared outside of UVa, beyond using data for a grant application and or publication, without a signed contract/MTA approved by the SOM Grants and Contracts office/ OSP or written confirmation that one is not needed.
- No specimens will be shared outside of UVa without a signed contract/MTA approved by the SOM Grants and Contracts office/ OSP or written confirmation that one is not needed.

Prisoners

If the original protocol/ IRB application stated that no prisoners would be enrolled in this study and subsequently a subject becomes a prisoner, the study team must notify the IRB immediately. The study team and IRB will need to determine if the subject will remain in the study. If the subject will remain in the study, the protocol will have to be re-reviewed with the input of a prisoner advocate. The prisoner advocate will also have to be involved in the review of future continuations, modifications or any other reporting such as protocol violations or adverse events.

Prisoner- Individuals are prisoners if they are in any kind of penal institution, such as a prison, jail, or juvenile offender facility, and their ability to leave the institution is restricted. Prisoners may be convicted felons, or may be untried persons who are detained pending judicial action, for example, arraignment or trial.

For additional information see the OHRP website at

<http://www.hhs.gov/ohrp/policy/populations/index.html>

Compensation in Case of Injury

If a subject requests compensation for an injury, the study team should notify the IRB-HSR ([name]) the UVa Health System Patient Relations Department ([name]). As a proactive courtesy, the study team may also notify UVa Health System Patient Safety and Risk Management ([name]).

On request, the study team should provide the Risk Management Office with the following information/documents:

- Subject Name and Medical Record Number

IRB-HSR# 17525 A Study of Patient-reported Outcomes in Patients with Lung or Esophageal Cancer

- Research medical records
- Research consent form
- Adverse event report to IRB
- Any letter from IRB to OHRP

Subject Complaints

During a research study, the study team may receive complaints from a subject. If the study team is uncertain how to respond to a complaint, or is unable to resolve it with the subject, the study team may contact the IRB-HSR ([name]), the UVa Health System Patient Relations Department ([name]).

Request for Research Records from Search Warrant or Subpoena

If the study team receives a request for research records from a search warrant or subpoena, they should notify UVa Health Information Services at [name]. It is important to notify them if information from the study is protected by a Certificate of Confidentiality.

